7.1 Demographic and Induction Baseline Characteristics

For the subjects in mITT and safety analysis set, demographic information and Induction Baseline values will be summarized by descriptive statistics. Categorical data will be summarized by number and percent; and quantitative data will be presented by n, mean, standard deviation, minimum value, median, and maximum value.

In general, continuous variables will be analyzed using analysis of variance (using SAS procedure 'PROC GLM') with treatment group as factor. Categorical variable will be analyzed using chi-square test or Fisher's exact test if $\geq 20\%$ of the cells have expected cell count < 5 .

The following demographic and Baseline values will be summarized.

Continuous Variables:

- Age (years)
- Body weight (kg)
- Height (cm)
- Body Mass Index (kg/m^2)
- Blood Pressure (systolic/diastolic) (mmHg)
- Pulse (bpm)
- Respiratory Rate (RPM)
- Temperature ($^{\circ}\text{C}$)
- IBDQ score

- CDAI
- SFPS
- Total SES-CD score
- Crohn's Disease Duration (years)
- hs-CRP mg/L
- WPAI and its components
- EQ-5D
- Abdominal Pain Rating Scale
- Bristol Stool Chart score
- Fecal calprotectin

Categorical Variables:

- Sex (male, female)
- Race
- Ethnicity
- Age (\leq median, $>$ median)
- Age (< 40 , 40 to < 65 , 65 to < 75 , ≥ 75)
- Baseline fecal calprotectin (\leq median, $>$ median)
- Baseline corticosteroid use (yes, no)
- Baseline immunosuppressant use (yes, no)
- hs-CRP at Baseline (< 10 and ≥ 10 mg/L)
- hs-CRP at Baseline (\leq median, $>$ median)
- Baseline fecal calprotectin (\leq median, $>$ median)
- Baseline fecal calprotectin (≤ 250 $\mu\text{g/g}$, > 250 $\mu\text{g/g}$)
- Crohn's disease severity (CDAI ≤ 300 , > 300) at Baseline
- Baseline CDAI (\leq median, $>$ median)
- Baseline SES-CD (\leq median, $>$ median)
- Prior infliximab use (or prior anti-TNF use for subjects randomized under original protocol) (yes, no)

- Weight (\leq median, $>$ median)
- Baseline albumin (\leq median, $>$ median)
- Disease duration (\leq median, $>$ median)
- Disease duration (\leq 3 years, $>$ 3 years)
- Tobacco use (user, ex-user, never used, unknown)
- Alcohol use (drinker, ex-drinker, non-drinker, unknown)
- Region (US, ex-US)

7.2 Medical History

Medical and Surgical History: A complete medical and surgical history (which includes CD-onset date), history of tobacco and alcohol use, will be obtained from each subject during the Screening period. Medical history will be summarized using body system and preferred term by treatment group. No statistical tests will be performed.

Chest X-Ray Results: All subjects undergo a standard chest X-ray of chest (including a posteroanterior [PA] and lateral view) at Screening period. Number and percent of subjects with presence or absence of finding for the previous TB infection, calcified granulomas, Pleural scarring/thickening, and other findings will be presented by treatment group. No statistical tests will be performed.

TB Test Results: Results of PPD skin test or QuantiFERON-TB Gold test at screening visit will be summarized. Induration will be summarized descriptively using n, mean, standard deviation, minimum values, median, and maximum values. The frequency distribution of induration ≥ 5 and < 5 will be provided. No statistical tests will be performed.

ECG Results: ECG results at screening will be presented as frequency distribution showing results as Normal, Abnormal (Not clinically significant), Abnormal (Clinically significant) and Unable to evaluate/missing. No statistical tests will be performed.

7.3 Previous Treatment and Concomitant Medications

Prior medications are those medications taken prior to the first dose of study drug. This includes medications with a start date before the first study drug administration date, regardless of the end date of these medications. Medications taken on the day of the first dose of study drug are not counted as prior medications.

Concomitant medications are those medications, other than study drug, taken after the first dose of study drug in Maintenance, which include medications with a start date prior to the Maintenance Baseline date which are continuing after Baseline and all medications with a start date between the Maintenance Baseline date and last study drug administration + 14 days.

Based on generic medication names, these categories of medications used by subjects before and during the study will be summarized by number and percent for mITT and safety analysis sets for the treatment groups. No statistical tests will be performed.

The number and percent of subjects using Crohn's disease specific medications (including corticosteroids [$0, \leq 10$ mg, ≤ 20 mg, or ≤ 30 mg prednisone equivalents], aminosalicylates, immunosuppressants, and antibiotics) at the Induction Baseline will be tabulated. In addition, the number and percent of subjects using any Crohn's disease specific medications including infliximab prior to Induction Baseline will be tabulated.

8.0 Patient Disposition

Subject disposition will be presented for subjects in the mITT and safety analysis sets using the following information by treatment group:

- Number and percent of subjects in various analysis sets by treatment group and by investigator and/or site number
- Number and percent of subjects completing 44-week Maintenance study
- Subject disposition including the number and percent of subjects who prematurely discontinued the Maintenance study by primary reason and by any reason

Summary of protocol deviations will be provided.

9.0 Study Drug Exposure and Compliance

Study drug exposure and compliance will be summarized using the mean, standard deviation, minimum, median, and maximum. Exposure to study drug (total patient years) will be summarized by treatment group.

The number of injections received at each schedule time point will be summarized with number and percent for each treatment group.

Study Drug Exposure (in Days) during the Maintenance Study:

- Date of last dose of Maintenance Study drug – Date of first dose of Maintenance Study drug + 14 days

Study Drug Compliance:

Treatment compliance will be summarized for each treatment group in the mITT population. The treatment compliance is defined as the number of injections actually taken by the subject divided by the number of injections planned to be taken by the subject during the Maintenance Study.

10.0 Efficacy Analysis

10.1 General Considerations

All statistical tests will be two-sided with the significance level of 0.05. Descriptive statistics will be provided. These include the number of observations, mean, standard deviation, minimum, median, and maximum for continuous variables; and number and percent for discrete variables. The analysis will be performed using SAS[®] Version 9.4 or later (SAS Institute Inc., Cary, NC, USA).

10.2 Efficacy Analyses

This section provides the details of the efficacy analysis for the Maintenance Study.

For these endpoints which are categorical variables, NRI method of imputation will be used for the missing values. LOCF will be used as a sensitivity analysis wherever applicable.

Both LOCF and OC analyses will be performed for continuous endpoints. The LOCF analysis is considered primary for inferential purposes. In addition, Mixed-Effect Model Repeated Measure (MMRM) will be applied as a sensitivity analysis, wherever appropriate, for the longitudinal continuous endpoints.

For endoscopy related endpoints, there will be no LOCF imputation as there is only one post-baseline endoscopy during Maintenance. OC will be used as a sensitivity analysis.

The difference in proportions of subjects between treatment groups will be analyzed using the two-sided Cochran-Mantel-Haenszel (CMH) test adjusted for induction treatment regimen, and decrease in SES-CD > 50% from Induction Baseline per central reading at Week 12. Additionally, the CMH-based two-sided 95% confidence interval (CI) for the difference in the proportions between the treatment groups will be calculated.

The difference in change from Induction Baseline between treatment groups will be analyzed using an ANCOVA model including factors of treatment, induction treatment regimen, decrease in SES-CD > 50% from Induction Baseline per central reading at Week 12 and Induction Baseline values. Parameter estimates with 95% confidence interval and *P*-value will be provided.

All efficacy endpoints for Maintenance Study are non-ranked.

- Proportion of subjects who achieve endoscopic response (SES-CD > 50% from Induction Baseline [or for a Induction Baseline SES-CD of 4, at least a 2 point

reduction from Induction Baseline]) at Week 56 among subjects with endoscopic response at Week 12

- Proportion of subjects who achieve endoscopic remission ($\text{SES-CD} \leq 4$ and at least a 2 point reduction versus Induction Baseline and no subscore greater than 1 in any individual variable) at Week 56 among subjects with endoscopic remission at Week 12.
- Proportion of subjects who achieve endoscopic remission ($\text{SES-CD} \leq 4$ and at least a 2 point reduction versus Induction Baseline and no subscore greater than 1 in any individual variable) at Week 56 among subjects with endoscopic response at Week 12.
- Proportion of subjects who achieve sustained clinical remission, $\text{CDAI} < 150$ at Week 56 among subjects with $\text{CDAI} < 150$ at Week 12.
- Proportion of subjects who achieve clinical remission ($\text{CDAI} < 150$) at Week 56.
- Proportion of subjects who achieve endoscopic remission ($\text{SES-CD} \leq 4$ and at least 2 point reduction versus Induction Baseline and no subscore greater than 1 in any individual variable) at Week 56.
- Proportion of subjects who achieve $\text{SES-CD} \leq 2$ at Week 56.
- Proportion of subjects with deep remission, $\text{CDAI} < 150$ at Week 56 and $\text{SES-CD} \leq 4$ and at least 2 point reduction versus Induction Baseline and no subscore greater than 1 in any individual variable at Week 56.
- Proportion of subjects who discontinued corticosteroid use and achieved clinical remission ($\text{CDAI} < 150$) at Week 56 among subjects taking corticosteroid at Induction Baseline.
- Proportion of subjects with endoscopic response (decrease $> 50\%$ SES-CD from Induction Baseline [or for a Induction Baseline SES-CD of 4, at least a 2 point reduction from Induction Baseline]) at Week 56.
- Change from Induction Baseline in fecal calprotectin level at Week 56.
- Proportion of subjects with $\text{hs-CRP} < 5 \text{ mg/L}$ and fecal calprotectin $< 250 \text{ } \mu\text{g/g}$ at Week 56.
- Proportion of subjects with $\text{CDAI} < 150$, $\text{hs-CRP} < 5 \text{ mg/L}$, and fecal calprotectin $< 250 \text{ } \mu\text{g/g}$ at Week 56.

- Proportion of subjects with CDAI < 150, hs-CRP < 5 mg/L, SES-CD \leq 4 and at least 2 point reduction versus Induction Baseline and no subscore greater than 1 in any individual variable, and fecal calprotectin < 250 μ g/g at Week 56.
- Proportion of subjects with endoscopic response, and \geq 50% decrease from Induction Baseline in hs-CRP or fecal calprotectin at Week 56.
- Proportion of subjects with endoscopic remission, and \geq 50% decrease from Induction Baseline in hs-CRP or fecal calprotectin at Week 56.
- Proportion of subjects with clinical remission, and \geq 50% decrease from Induction Baseline in hs-CRP or fecal calprotectin at Week 56.
- Proportion of subjects with clinical response (decrease in CDAI \geq 70 points from Induction Baseline) at Week 56.
- Proportion of subjects with clinical response (decrease CDAI \geq 70 points from Induction Baseline) at each scheduled visit in Maintenance Study.
- Proportion of subjects with enhanced clinical response (decrease CDAI \geq 100 points from Induction Baseline) at each scheduled visit in Maintenance Study.
- Proportion of subjects who discontinue corticosteroid use at each scheduled visit in Maintenance Study among subjects taking corticosteroid at Induction Baseline.
- Proportion of subjects who achieve a composite subtotal score of SFPS < 50 at Week 56 who had an SFPS \geq 100 at Induction Baseline.
- Proportion of subjects who achieve SES-CD \leq 3 and at least a 2 point reduction versus Induction Baseline and no subscore greater than 1 in any individual variable at Week 56.
- Proportion of subjects with SES-CD = 0 at Week 56.
- Change from Induction Baseline in fecal calprotectin level at each scheduled visit in Maintenance Study.
- Change from Induction Baseline in hs-CRP at each scheduled visit in Maintenance Study.

- Change in IBDQ total score and individual IBDQ domain scores (bowel, emotional, social, systemic) from Induction Baseline at each scheduled visit in Maintenance Study.
- Change in WPAI from Induction Baseline at each scheduled visit in Maintenance Study.
- Change in EQ-5D from Induction Baseline at each scheduled visit in Maintenance Study.
- Change in CDAI from Induction Baseline at each scheduled visit in Maintenance Study.
- Change in SFPS from Induction Baseline at each scheduled visit in Maintenance Study.
- Change in Abdominal Pain Rating Scale score from Induction Baseline at each scheduled visit in Maintenance Study.
- Change in Bristol Stool Chart score from Induction Baseline at each scheduled visit in Maintenance Study.
- Proportion of subjects who achieve CDAI remission ($CDAI < 150$) at each scheduled visit in Maintenance Study.
- Proportion of subjects who achieve SFPS remission ($SFPS < 50$) at each scheduled visit in Maintenance Study.
- Proportion of subjects with major CD related event (e.g., hospitalization, bowel surgery, abscess drainage) in Maintenance Study.
- Proportion of subjects with no draining fistulas at Week 56 among subjects with draining fistula at Induction Baseline.
- Proportion of subjects in each treatment group with $> 50\%$ reduction from Induction Baseline in the number of draining fistulas at Week 56 among subjects with draining fistula at Induction Baseline.
- Resolution of extra-intestinal manifestations at each scheduled visit in Maintenance Study.
- Proportion of subjects with an SES-CD decrease of ≥ 3 points compared to Induction Baseline at Week 56.
- Proportion of subjects who achieve symptomatic remission, defined as average daily stool frequency ≤ 2.8 (and not worse than Induction Baseline) and

average daily abdominal pain ≤ 1.0 (and not worse than Induction Baseline), at each scheduled visit in Maintenance Study among subjects with Induction Baseline SF ≥ 4.0 and/or AP ≥ 2.0 .

- Proportion of subjects who achieve symptomatic response, defined as average daily stool frequency at least 30% reduction from Induction Baseline and average daily abdominal pain not worse than Induction Baseline or average daily abdominal pain at least 30% reduction from Induction Baseline and average daily stool frequency not worse than Induction Baseline, at each scheduled visit in Maintenance Study among subjects with Induction Baseline SF ≥ 4.0 and/or AP ≥ 2.0 .
- Time to dose escalation in Maintenance Study.
- Proportion of subjects with Inflammatory Bowel Disease Questionnaire (IBDQ) response (increase ≥ 16 points from Induction Baseline) at each scheduled visit in Maintenance Study.
- Proportion of subjects with IBDQ remission (IBDQ ≥ 170 points) at each scheduled visit in Maintenance Study.
- Proportion of subjects achieving response in IBDQ Bowel Symptom domain (increase of IBDQ bowel symptom domain score ≥ 8) at each scheduled visit in Maintenance Study.
- Proportion of subjects achieving response in IBDQ fatigue item (increase of IBDQ fatigue item score ≥ 1) at each scheduled visit in Maintenance Study.
- Proportion of subjects requiring dose escalation to weekly dosing during Maintenance Study.
- Proportion of subjects who achieve clinical remission (CDAI < 150) at Week 56 among subjects requiring dose escalation to weekly dosing during Maintenance Study.
- Proportion of subjects who achieve endoscopic response (decrease $> 50\%$ SES-CD from Induction Baseline [or for an Induction Baseline SES-CD of 4, at least a 2 point reduction from Induction Baseline]) at Week 56 among subjects requiring dose escalation to weekly dosing during Maintenance Study.
- Proportion of subjects who achieve endoscopic remission (SES-CD ≤ 4 and at least a 2 point reduction versus Induction Baseline and no subscore greater

than 1 in any individual variable) at Week 56 among subjects requiring dose escalation to weekly dosing during Maintenance Study.

Major CD related events will be identified by review of serious adverse events (SAEs) according to the hospitalization adjudication charter. *P* values from both Log-rank test and Cox proportional hazards model will be provided.

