**Statistical Methods (Continued):**

**Efficacy (Continued):**

Secondary efficacy variables for the Induction Study are divided into two groups. The first group includes ranked secondary endpoints, which are ranked by clinical importance. Statistical significance is assessed at significance level of 0.050 (2-sided) in ranked endpoint order until the significance level exceeds 0.05. No additional statistically significant treatment differences may be declared after the first ranked endpoint fails to achieve statistical significance at a two-sided significance level of 0.05. The second group includes all other secondary variables.

In general, continuous secondary efficacy variables, including all efficacy variables for Maintenance Study, will be analyzed using Analysis of Covariance (ANCOVA) model including factor for treatment group, stratification factors and Baseline values, whereas CMH test stratified by stratification factors is used for categorical endpoints. NRI for missing data will be used for categorical endpoints. Both last observation carried forward (LOCF) and observed case (OC) analyses will be performed for continuous endpoints. The LOCF analysis is considered primary for inferential purposes. In addition, Mixed-Effect Model Repeated Measure (MMRM) will be applied, wherever appropriate, as a sensitivity analysis for the longitudinal continuous endpoints.

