Week 56/PD visit. Sites should also perform an SES-CD assessment and record findings on the provided SES-CD score sheet, refer to [Appendix M](#). The findings should be entered in the appropriate eCRF. Videos from Screening endoscopies from subjects the Investigator believes are eligible for the trial (i.e., subjects with an SES-CD  $\geq 6$ , excluding the presence of narrowing component, (or SES-CD  $\geq 4$ , excluding the presence of narrowing component, for patients with disease limited to the ileum), and all Week 12 and Week 56/PD endoscopies conducted will undergo central review. Two primary central reviewers will evaluate the data and provide their score. If the SES-CD scores are discrepant between the two readers, a third central reviewer will review the video and choose between the first and second reviewers' scores. The third reviewer's choice between the reviewers' scores will be considered final. This process will apply to all video endoscopies where the first and second reviewers do not agree. The adjudicator's assessment will be considered final. If, in the opinion of the Investigator, the Screening endoscopy does not indicate the SES-CD criteria confirming study eligibility, the subject should be screen-failed and the video should not be sent for central review. Endoscopic eligibility will be determined by the central reviewers. The same endoscopist, where possible, should perform all endoscopies.

The endoscopy during the Screening Period or endoscopy performed within 45 days before Baseline and Week 56/PD will be used to provide the endoscopy subscores for calculating the Simplified Endoscopic Score (SES-CD) at Screening, Week 12, and Week 56/PD, refer to [Appendix M](#). The SES-CD values provided by the central reader will be used for all endpoint analyses.

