#### **8.1.4.3 Efficacy Variables for Maintenance Study**

For categorical endpoints, the difference in proportions of subjects between treatment groups will be analyzed using the CMH test adjusted for stratification variables. Additionally, the two-sided 95% confidence interval for the difference in proportions will be provided. The non-responder imputation will be used for subjects with missing data at the endpoint evaluated. The last observation carried forward (LOCF) method will also be used as the sensitivity analyses for the primary and ranked secondary endpoints.

Change from Baseline in continuous ranked and non-ranked secondary endpoints will be analyzed using an ANCOVA model including factors of treatment and adjusting for the baseline values and the stratification variables. For analyses of changes from Baseline

variables, both LOCF and OC analyses will be performed. The LOCF analysis is considered primary for inferential purposes. In addition, Mixed-Effect Model Repeated Measure (MMRM) will be applied, wherever appropriate, as a sensitivity analysis for the longitudinal continuous endpoints.

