5.2 Variables Used for Stratification of Re-Randomization

At Week 12, subjects are re-randomized in a 1:1 ratio to one of two double-blinded exploratory treatment regimens (clinically adjusted [CA] regimen and adalimumab therapeutic drug monitoring [TDM] regimen). The re-randomization at Week 12 is stratified by induction treatment regimen, clinical response (CR-70) status at Week 12, and decrease in SES-CD > 50% from Baseline per the site investigator reading at Week 12. Among subjects achieving decrease in SES-CD > 50% from Baseline at Week 12, the randomization is further stratified by achievement of an SES-CD ≤ 4 and at least a 2 point reduction versus baseline and no subscore greater than 1 in any individual variable using the Week 12 SES-CD value provided by the site.

The randomization schedule was prepared by the Statistics Department of AbbVie.

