Subjects in whom systemic corticosteroids were used at Induction Baseline and initiated rectal corticosteroids during the study will be censored for efficacy assessment, regardless of rectal corticosteroid dose.

The equivalent steroid dose will be determined based on the table below:

Corticosteroid	Equivalent Dose (mg)
Cortisone	25
Hydrocortisone	20
Prednisone	5
Prednisolone	5
Triamcinolone	4.0
Methylprednisolone	4.0
Betamethasone	0.75
Dexamethasone	0.75
Budesonide	1
Beclomethasone	5
Beclometasone	5

Definition of Missing Data Imputation

The following imputation methods will be used to impute missing values in the efficacy analyses. In addition, an observed case analysis will be performed.

Non-Responder Imputation (NRI)

The NRI approach is used for binary efficacy variables. These variables can take values of 'Achieved' or 'Not Achieved' or may be missing for any reason including discontinuation from study. According to the NRI imputation approach, all missing values will be considered as 'Not Achieved.'

Last Observation Carried Forward (LOCF)

For all variables (categorical variables and continuous variables), the following rules will be used for the LOCF approach:

1. Maintenance Baseline and Pre-Maintenance Baseline values will not be used to impute the missing Post-Maintenance Baseline values.

2. Missing values after Study Day 1 will be imputed using the latest non-missing values after Day 1 and prior to the missing value. If there are no non-missing values after Maintenance Baseline, then the LOCF value will be missing.

Mixed-Effect Model Repeated Measure (MMRM)

The MMRM model will be used for continuous efficacy variables with longitudinal data as a sensitivity analysis. The MMRM model includes the Induction baseline values as covariate; randomization strata, region (US versus non-US), treatment, time point and treatment-by-time point interaction as fixed effects; and subjects within treatment as random effect. An unstructured (co)variance structure will be used to model the within-subject error. The comparison at a time point will be the contrast between treatments at that time point.

Observed Case (OC)

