Both LOCF and OC analyses will be performed for continuous endpoints. The LOCF analysis is considered primary for inferential purposes. In addition, Mixed-Effect Model Repeated Measure (MMRM) will be applied as a sensitivity analysis, wherever appropriate, for the longitudinal continuous endpoints.

For endoscopy related endpoints, there will be no LOCF imputation as there is only one post-baseline endoscopy during Induction. Only OC will be used as a sensitivity analysis.

The difference in proportions of subjects between treatment groups will be analyzed using the two-sided Cochran-Mantel-Haenszel (CMH) test adjusted for hs-CRP at Baseline (< 10 and ≥ 10 mg/L), prior infliximab use (or prior anti-TNF use for subjects randomized under original protocol), and Crohn's disease severity (CDAI ≤ 300 , > 300) at Baseline. Additionally, the CMH-based two-sided 95% confidence interval (CI) for the difference in the proportions between the treatment groups will be calculated. An exact CMH test will be used to handle zero cells.

The difference in change from Baseline between treatment groups will be analyzed using an ANCOVA model including factors of treatment, hs-CRP at Baseline, prior infliximab use (or prior anti-TNF use for subjects randomized under original protocol), and Crohn's disease severity at Baseline, and Baseline values. Parameter estimates with 95% confidence interval and *P*-value will be provided.

All additional efficacy endpoints will be non-ranked.

- Proportion of subjects with clinical response (decrease CDAI ≥ 70 points from Baseline) at each scheduled visit in Induction Study.

- Proportion of subjects with enhanced clinical response (decrease CDAI ≥ 100 points from Baseline) at each scheduled visit in Induction Study.
- Proportion of subjects who discontinue corticosteroid use at each scheduled visit in Induction Study among subject taking corticosteroids at Baseline.
- Proportion of subjects who achieve a composite subtotal score of SFPS < 50 at Week 12 who had an SFPS ≥ 100 at Baseline.
- Proportion of subjects who achieve a composite subtotal score of SFPS < 50 at Week 4 who had an SFPS ≥ 100 at Baseline.
- Proportion of subjects who achieve SES-CD ≤ 3 and at least a 2 point reduction versus baseline and no subscore greater than 1 in any individual variable at Week 12.
- Proportion of subjects with SES-CD = 0 at Week 12.
- Change from Baseline in fecal calprotectin level at each scheduled visit in Induction Study.

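### In two endpoints among Week 12 endoscopic responders, the Maintenance CMH adjusts in effect for induction regimen alone, because SAP 10.2 drops the SES-CD ≤ 4 level used at re-randomisation

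*SAP*

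**What the plan says.** - **Re-randomisation strata** (Maintenance SAP 5.2; protocol 8.3): induction regimen, Week 12 CR-70 status, and "decrease in SES-CD > 50% from Baseline per the site investigator reading at Week 12". Within the group with that decrease, "the randomization is further stratified by achievement of an SES-CD" ≤ 4, with at least a 2-point reduction and no subscore above 1, again on the site's score.
- **Protocol analysis rule** (8.1.4.3): categorical Maintenance endpoints "will be analyzed using the CMH test adjusted for stratification variables". The synopsis describes the models in the same way: "including factor for treatment group, stratification factors and Baseline values, whereas CMH test stratified by stratification factors is used for categorical endpoints".
- **SAP analysis rule** (Maintenance SAP 10.2): the CMH test is "adjusted for induction treatment regimen, and decrease in SES-CD > 50% from Induction Baseline per central reading at Week 12". The ANCOVA uses the same two factors plus the Induction Baseline value.
- **Elsewhere in the SAPs:** the Maintenance MMRM (SAP 6.0) keeps "randomization strata, region (US versus non-US), treatment, time point and treatment-by-time point interaction as fixed effects". The Induction SAP (10.3) carries out the matching protocol sentence with the factors used at randomisation, and even follows the factor in force under the first protocol: "prior infliximab use (or prior anti-TNF use for subjects randomized under original protocol), and Crohn's disease severity".
- **Log of differences from the protocol** (Maintenance SAP 12.1): one corrected endpoint and four added endpoints, all in Section 10.2. It has no entry on adjustment factors.
- **Endoscopic response** (Maintenance SAP 6.0): a centrally read decrease above 50%, or at least 2 points when the Induction Baseline score is 4.

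**The concern.** A stratification level chosen because it should predict outcome is normally carried into the analysis. Here the SES-CD ≤ 4 level is lost. In most Maintenance endpoints the remaining SES-CD factor still separates subjects with and without a decrease above 50%, so part of the prognostic information is kept. In the two endpoints restricted to Week 12 endoscopic responders, the restriction and the adjustment factor are almost the same criterion, so the factor has nothing left to separate. The dropped level still varies among these subjects. It is also the Week 12 counterpart of one of the two outcomes, Week 56 remission.

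What is at stake is the width of the confidence interval. Maintenance has no sample-size calculation (SAP 4.3), so interval width is the natural measure of what these comparisons can show.

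**Working it through.** The plan gives no Maintenance sample size or power, so there is no figure to reproduce.

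**1. Count of strata.** Re-randomisation has 2 (regimen) × 2 (CR-70) × 3 (SES-CD status) = 12 cells. The mITT set contains only CR-70 responders (SAP 5.1), which leaves 2 × 3 = 6. SAP 10.2 uses 2 × 2 = 4. Omitting CR-70 has no effect.

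**2. When can a responder lack a decrease above 50%?** Only through the exception for a Baseline score of 4. A reduction of at least 2 points from 4 gives Week 12 scores of 0, 1 or 2, which are decreases of 100%, 75% and exactly 50%. Only 4 to 2 fails the above-50% test. Enumerating Baseline totals 4–60 against all Week 12 totals finds the same single pair. Among responders the SAP factor is therefore constant apart from that pair. The ≤ 4 level is not: a responder's Week 12 score may be above or below 4.

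**3. Size, closed form.** Allocation is 1:1 within strata. Let level *k* hold a share *w_k* of responders and have Week 56 rate *p_k*, with p̄ = Σ w_k p_k. Near the null,

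SE without the level ÷ SE with the level = √[ p̄(1 − p̄) ÷ Σ w_k p_k(1 − p_k) ].

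Worked case: shares 25:30 (not in remission : in remission at Week 12) and rates 30% and 65%.
- p̄ = (25 × 0.30 + 30 × 0.65)/55 = 0.4909, so p̄(1 − p̄) = 0.2499.
- Σ w_k p_k(1 − p_k) = (25 × 0.2100 + 30 × 0.2275)/55 = 0.2195.
- Ratio = √(0.2499/0.2195) = 1.067, which is 6.7% wider.

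Excess SE for other inputs (all rates and shares are assumptions):

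| Week 56 rate, not in remission / in remission at Week 12 | 25:30 | 35:20 | 20:35 |
|---|---|---|---|
| 35% / 50% | 1.2% | 1.1% | 1.1% |
| 30% / 65% | 6.7% | 6.3% | 6.2% |
| 30% / 75% | 12.0% | 11.0% | 11.3% |

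With 45% / 65% and equal shares the result is √(0.2475/0.2375) = 1.021, or 2.1%.

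**4. Size, simulation.** Assumed inputs: mITT of 300, hence about 165 responders (55%); induction 60:40; permuted blocks within the six site-read strata; site–central disagreement from none to about 30%. Over 15 settings of 3,000 trials, the SAP factors gave an SE 0.7–13.3% larger than stratifying by induction regimen and central-read Week 12 remission. Both options use the central read, so this isolates the dropped level. In one mid-range setting (30/65%, reads equally accurate, 15% disagreement) the 95% half-width was 14.6 points against 13.8.

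**5. Validity and power.** Under the null, the test with the SAP factors rejected in 2.8–5.2% of trials. A separate simulation of 150–250 responders, half in remission at Week 12, with rates of 65/45% or 75/35%, gave 2.9–5.4% without the level and 4.3–5.6% with it. For a true 15-point difference, restoring the level changed power by about 0 to 7 points (for example 46% to 54% at n = 150, with full agreement and the larger gap). The low null rates are expected: allocation was balanced on the level, so an analysis that ignores it overstates the SE.

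**The case against.** The case for leaving the plan alone is substantial. Maintenance is exploratory, its endpoints are non-ranked, and no multiplicity control or power target depends on them. Only two of more than 40 listed endpoints are affected. The upper figures need a 45-point gap in Week 56 rates and close agreement between readers, and no input has a source in the documents. Protocol 8.1 leaves full details to the SAP, and the synopsis sentence is introduced as a general rule. Section 8.1.4.3 also mentions primary and ranked endpoints, which Maintenance lacks, so it looks like reused Induction text. All of this stands, and it is why the point is minor. It does not explain why the factor should be kept where it has almost no content.

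A reader might infer more than the documents support:

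- *That the Maintenance comparisons are biased or have inflated type I error.* They do not. The planned test is nominal to mildly conservative.
- *That using the central read is itself an error.* Protocol 5.3.1.1 says "The SES-CD values provided by the central reader will be used for all endpoint analyses", so it is a defensible choice.
- *That every Maintenance endpoint should use the six site-read strata.* Over the full mITT set, the SAP factors gave an SE between 1.2% smaller and 3.3% larger than the recorded strata when the central read drives outcome, so the gain may be nil. No gain is shown for the ANCOVA. Six strata also become sparse in small subsets, such as Baseline steroid users or subjects with draining fistulas.
- *That the endpoint among Week 12 endoscopic remitters is affected in the same way.* There the centrally read ≤ 4 level is constant by definition, so nothing would be recovered.

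**Conclusion.** The point holds in a limited form. SAP 10.2 omits a stratification level that protocol 8.1.4.3 would carry into the CMH test. In the two responder-only endpoints the SES-CD factor that remains is empty except for subjects going from 4 to 2. That much follows from the documents alone.

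The size rests on assumed Week 56 rates. The excess SE is about 1–2% if Week 12 remission shifts the Week 56 rate by 15–20 points, 6–7% at 30/65%, and 11–12% at 30/75%. A 6.7% larger SE corresponds to about 14% more subjects for the same precision (1.067² = 1.138). Validity is not in question and no confirmatory conclusion depends on these endpoints. The missing entry in SAP 12.1 is a gap in the record whatever the size of the precision loss. Severity: minor.

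**What to change.** 1. In Maintenance SAP 10.2, for Week 56 endoscopic response and Week 56 endoscopic remission among Week 12 endoscopic responders only, stratify the CMH test and its confidence interval by induction regimen × central-read Week 12 endoscopic remission (yes/no). Leave the factors for the other endpoints as they are.
2. In SAP 12.1, record that the Maintenance CMH and ANCOVA factors differ from the re-randomisation strata in two respects: the ≤ 4 level is dropped, and the central reading replaces the site reading.
3. Optionally, analyse these two endpoints by the recorded site-read strata as a sensitivity analysis.

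The cost is SAP wording; the central scores are already in the database. The downside is four strata where there are now in effect two. With about 165 responders, a 60:40 induction split and a 25:30 mix (assumed), the smallest stratum holds about 165 × 0.40 × 25/55 = 30 subjects, so sparseness is negligible.
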